6.5 Subject Compliance

Subjects must be instructed to bring their unused IP and empty/used IP packaging to every visit. Drug accountability must be assessed at the container/packaging level for unused IP that is contained within the original tamper-evident sealed container (eg, blister pack) or at the individual count level for opened containers/packaging. The pharmacist/nominated person will record details on the drug accountability form.

7. STUDY PROCEDURES

7.1 Study Schedule

This study will consist of a screening period of up to 56 days (the screening period may be minimally extended under special circumstances only with the explicit approval of the medical monitor), a 48-week Treatment period, and a Follow-up visit 4 weeks after treatment ends. A detailed display of all study procedures is provided in [Table 1](#).

Patients will be assessed according to the following schedule:

- Screening – Visit 1 (Weeks -8 to 0 [Day -56 to Day -1])
- Baseline – Visit 2 (Week 0 [Day 0])
- Treatment and Assessments – Visits 3 through 9 (Week 2 through Week 48)
- Follow-up – Visit 10 (Week 52, 4 weeks after completion of dosing)

7.1.1 Screening (Visit 1)

Screening procedures must be completed within 56 days prior to randomization for the first dose of the IP. The screening period may be minimally extended under special circumstances only with the explicit approval of the medical monitor. At the screening visit, considered Visit 1 (Week -8 to 0, Day -56 to -1), all screening assessments and procedures are to be performed by the principal investigator or a qualified designee. See [Table 1](#) for a complete list of screening procedures to be performed.

Written, signed, and dated informed consent from the subject prior to the performance of any study-related procedures must be obtained by the principal investigator or a designee. A copy of the signed informed consent form must be given to the subject for their records.

The following screening procedures should be assessed at the beginning of the visit window, preferably between Day -56 and Day -49: inclusion/exclusion criteria, collection of subject information (demographics, medical and medication history AEs, and concomitant medications), a physical examination including vital signs, height, weight, and waist/hip measurements; collection of blood and urine samples for screening and safety assessments, performance of an electrocardiogram (ECG), and scheduling of MRI and liver biopsy. MRI and liver biopsy (if one has not been completed in the previous 6 months) should be performed with sufficient time to ensure results are received prior to the baseline visit.

A screen failure is a subject who has given informed consent and failed to meet the inclusion and/or met at least 1 of the exclusion criteria and has not been randomized or administered the IP. Subjects cannot be rescreened once they have been designated as a screen failure. However, a subject's abnormal screening lab results may be repeated for confirmation before designating a subject as a screen failure.

7.1.2 Baseline (Visit 2)

Following the screening visit, subjects will return to the clinic within 56 days for Visit 2, (considered Week 0, Day 0), for baseline assessments including review of the inclusion/exclusion criteria, adverse events, and concomitant medications; physical examination with vital signs, weight, and waist/hip measurements; ECG; collection of blood and urine samples; stool assessment; and completion of the patient-reported outcome (PRO) EuroQol-5 Dimension-5 Level Questionnaire (EQ-5D-5L) survey. After completion of these assessments, subjects are randomized using Interactive Response Technology (IRT) to 1 of 4 treatment arms receiving volixibat 5 mg, 10 mg, or 20 mg, or PBO. The initial supply of study drug is dispensed to ensure adequate daily dosing until the next scheduled study visit.

7.1.3 Treatment and Assessment Period (Visits 3 through 9/EOS)

During the 48 weeks of double-blind treatment, 7 clinic visits are scheduled to occur as follows:

- Visit 3 - Week 2, Day 14 (+/- 3 days)
- Visit 4 - Week 4, Day 28 (+/- 3 days)
- Visit 5 - Week 8, Day 56 (+/- 5 days)
- Visit 6 - Week 12, Day 84 (+/- 5 days)
- Visit 7 - Week 24, Day 168 (+/- 7 days) – Interim Analysis
- Visit 8 - Week 36, Day 252 (+/- 7 days)
- Visit 9 - Week 48, Day 336 (+/- 7 days) – End of Study

Subjects are reminded not to eat and not to take their study drug on the day of scheduled study visits prior to completion of assessments. They should bring their study drug with them to the visit. All assessments should be completed at least 30 minutes prior to administration of the IP. IP should be taken 30 minutes prior to the first meal of the day containing approximately 10-20 grams of fat.

The Schedule of Assessments provided in [Table 1](#) details the procedures to be completed at each visit. All Treatment visits (3 through 9) will include weight and waist/hip measurements, assessment of vital signs, and blood sampling for completion of biochemistry, hematology, serum glucose, lipid panel, HbA1c, and serum liver-related blood tests. At all visits, adverse events, and concomitant medications will be collected for all subjects, and female subjects of childbearing potential will have a urine pregnancy test. Subjects will return containers of unused study drug for assessment of accountability and compliance which will be documented in the IRT. New supplies of study drug will be dispensed at Visits 3 through 8.

Additional assessments will also occur less frequently during the Treatment Period for vitamin A, vitamin D, vitamin E, vitamin K via PT/INR, insulin, thyroid testing, urinalysis, ECG, physical examinations, stool assessment, and completion of the EQ-5D-5L.

An MRI will be repeated at Visit 7 for the 24-week IA and at Visit 9 (Week 48) for all subjects. A final liver biopsy will be performed at Visit 9 (Week 48) for all subjects unless a subject discontinues prior to Week 44, in which case the EOS liver biopsy is not required.

7.1.4 Follow-up (Visit 10)

The follow-up period for this protocol is 4 weeks after the last dose of study drug with a final Follow-up visit scheduled for Week 52. Procedures to be completed at this final visit include physical examination, weight, waist/hip measurements, vital signs, samples for biochemistry and hematology, serum glucose, lipid panel, HbA1c, serum liver-related blood tests, insulin, thyroid testing, stool assessment, and urine pregnancy test (for women of childbearing potential). Adverse events and concomitant medications will be recorded. All AEs and SAEs that are not resolved at the time of this contact will be followed to closure (see Section 8.1).

7.1.5 Additional Care of Subjects after the Study

No after care is planned for this study.

7.2 Study Evaluations and Procedures

All assessments and procedures are to be performed by the Investigator or a qualified designee who has been trained in the protocol. Assessments are to be performed according to the schedules shown in [Table 1](#). If a subject terminates the study early, the CRC will make reasonable effort to perform the EOS and safety follow-up assessments and procedures for the subject's safety and well-being.

7.2.1 Demographic and Other Baseline Characteristics

Demographic details will be obtained at screening and recorded on the eCRF. Data collected will include age, gender, ethnicity, height, and weight.

7.2.2 Efficacy

7.2.2.1 Liver Biopsy

Liver biopsies will provide histologic data for confirmation of the diagnosis of NASH, assessment and grading of NASH activity, and scoring of steatosis, lobular inflammation, ballooning, as well as fibrosis and additional features (see [Appendix 2](#) and Laboratory Manual for additional information).

7.2.2.2 MRI

The presence of $\geq 5\%$ steatosis on screening MRI from a centrally read radiologist will be performed either during the screening period or within 6 months prior to the first visit. Steatosis is assessed by MRI hepatic fat fraction. The Week 24 MRI will be conducted for subjects in the IA set only.

7.2.3 Safety

7.2.3.1 Medical History and Medications

Medical history including important medical events and concomitant medication and illnesses will be obtained at screening and will be recorded on the eCRF. Any existing medical condition present prior to the time of randomization should be reported as medical history

7.2.3.2 Physical Examination

A complete physical examination will be performed with a thorough review of body systems at screening, baseline prior to randomization, and at study visits specified in [Table 1](#). Physical examinations will include a review of the subject's general appearance, as well as evaluation of the body systems including:

- Eyes, ears, nose, throat
- Lymph nodes
- Cardiovascular
- Skin
- Abdomen
- Neurological
- Spine and extremities

Abnormalities identified at the screening visit (Visit 1) will be documented in the subject's source documents and on the medical history eCRF. Changes after the screening visit (Visit 1) will be captured as AEs on the AE eCRF page, if deemed clinically significant by the investigator.

Height will be measured at the screening visit only while weight and waist and hip circumference will be recorded at all study visits. BMI will be calculated programmatically.

7.2.3.3 Adverse Event Collection

At each study visit, subjects will be questioned in a general way to ascertain if AEs have occurred since the previous visit (eg, "Have you had any health problems since your last visit?"). Adverse events are collected from the time informed consent is signed. (Please refer to Section 8, Adverse and Serious Adverse Events Assessment.)

7.2.3.4 Vital Signs

Vital signs include oral or tympanic temperature, sitting blood pressure, pulse, and respiratory rate. Blood pressure should be determined by cuff (using the same method, the same arm, and in

the same position throughout the study). Any deviations from baseline (Visit 2) vital signs which are deemed clinically significant in the opinion of the investigator are to be recorded as an AE.

7.2.3.5 Clinical Laboratory Evaluations

All clinical laboratory assays will be performed according to the central laboratory's normal procedures. Reference ranges supplied by the central laboratory will be used to assess the clinical laboratory data for clinical significance and out-of-range pathological changes. The investigator should assess out-of-range clinical laboratory values for clinical significance, indicating if the value(s) is/are not clinically significant or clinically significant. Clinically significant findings should be evaluated for recording as adverse events on the eCRF. Abnormal clinical laboratory values, which are unexpected or not explained by the subject's clinical condition, may, at the discretion of the investigator or sponsor, be repeated as soon as possible until confirmed, explained, or resolved.

The following clinical laboratory assessments will be performed:

Biochemistry

- Albumin (ALB)
- Alkaline phosphatase (ALP)
- Alanine aminotransferase (ALT; SGPT)
- Aspartate aminotransferase (AST; SGOT)
- Blood urea nitrogen (BUN)
- C4
- Calcium (Ca)
- Bicarbonate (CO₂)
- Chloride (Cl)
- Creatinine
- Creatine kinase
- Gamma glutamyl transferase (GGT)
- Glucose
- Lactate dehydrogenase (LDH)
- Magnesium (Mg)
- Phosphate (P)
- Potassium (K)
- Sodium (Na)
- Total and direct bilirubin
- Total cholesterol
- Protein
- Triiodothyronine (T₃)
- Thyroid-stimulating hormone (TSH)
- Triglycerides
- Uric acid

Hematology

- Hemoglobin
- Hematocrit
- Mean corpuscular hemoglobin (MCH)
- Mean corpuscular volume (MCV)
- Platelets
- Red blood cell (RBC)
- White blood cell (WBC) count with differential
- Prothrombin time (PT)
- Activated partial thromboplastin time (aPTT)
- International normalized ratio (INR)

Urinalysis

- Appearance (clarity and color)
- Bilirubin
- Blood
- Glucose
- Ketones
- Leukocyte esterase
- Microscopic examination of sediment
- Nitrite
- pH
- Protein
- Specific gravity
- Urobilinogen
- Oxalate

7.2.3.6 Additional Laboratory Assessments

Laboratory samples will be collected and assessed for:

- HIV testing and assessment of Hepatitis B/C including HBcAb, HBsAg, HBVDNA, and HCVA_b, and HCVRNA will occur at the screening visit only
- Lipid panel including fasting total cholesterol, HDL-C, LDL-C, and triglycerides at each scheduled study visit (Visits 1 through 10)
- HbA1c will be tested at every scheduled visit (Visits 1 through 10)
- Full coagulation panel will be done at screening and baseline, but only PT/INR is required at remaining time points at Visits 4, 7, and 9
- Insulin will be tested at screening, baseline, at Visit 4 and Visits 6 through 10
- HOMA-IR and HOMA-%B: will be calculated programmatically from serum glucose tested at screening, baseline, Visits 7, 9, and 10

- Vitamin A, Vitamin D, Vitamin E, and Vitamin K (via PT/INR) will be tested at screening, baseline, and Visits 4, 7, and 9
- Thyroid testing including TSH and T3 will be tested at screening, baseline, and Visits 4, 6, 7, 9, and 10
- C4 samples will be collected at baseline and Visits 6, 7, 9, and 10

7.2.3.7 Pregnancy Test

A urine pregnancy test is performed on all females of child-bearing potential at the screening visit (Visit 1), baseline visit (Visit 2), at each Treatment visit (Visits 3 through 9) and at the Final visit (Visit 10), or if pregnancy is suspected, or on withdrawal of the subject from the study. A positive urine pregnancy test must be followed with a serum pregnancy test performed by the central laboratory. Additional testing can be performed at the investigator's discretion. Also, refer to Section 8.1.7.

7.2.3.8 Drug and Alcohol Testing

A urine screen for drugs of abuse and blood test for alcohol will be performed at screening and baseline as described in [Table 1](#). Additional drug and alcohol screens may be performed at the investigator's discretion.

Urine samples are to be tested for amphetamines, barbiturates, benzodiazepines, cannabinoids, cocaine, methadone, opiate metabolite, and phencyclidine.

Results of drug and alcohol screens will be reviewed and verified by the study monitor, but will not be collected in the eCRF database.

Any positive result for drugs of abuse at the screening or baseline visits may exclude the subject from further participation in the study. A positive test for drugs of abuse or alcohol done at the investigator's discretion discovered at any time during the study will be grounds for study discontinuation.

7.2.3.9 Electrocardiogram

An ECG (12-lead) will be performed at the times specified in [Table 1](#) in accordance with the clinical site's standard practice(s) and equipment supplied by the CRC. Recordings of ECGs will be read locally at the clinical site by the investigator or designee. The ECG will include assessments of heart rate and PR, RR, QRS, and QT intervals. Identification of any clinically significant findings and/or abnormalities will be recorded on the eCRF.

7.2.3.10 Health-related Quality of Life Assessments

The EuroQol (EuroQol. 2016. Available at: <http://www.euroqol.org>. [Accessed 17 February 2016]) EQ-5D-5L ("EQ-5D") is a widely used standardized questionnaire that assesses generic HRQoL and is also recommended for health-economic evaluations. The EQ-5D includes two components: a descriptive profile and a visual analogue scale (VAS). The descriptive profile

includes five dimensions (ie, pain/discomfort, mobility, usual activities, self-care and anxiety/depression), each with five levels (ie, no problems, slight problems, moderate problems, severe problems, extreme problems). An EQ-5D index can also be derived from the data which summarizes health status using a single value (ie, health-state utility). The psychometric properties of the EQ-5D-5L have been established and well documented (see [Appendix 3](#)).

7.2.3.11 Volume of Blood to be Drawn from Each Subject

During this study, it is expected that approximately 146 mL of blood will be drawn from all subjects, regardless of sex.

Note: The amount of blood to be drawn for each assessment is an estimate. The amount of blood to be drawn may vary according to the instructions provided by the manufacturer or laboratory for an individual assessment; however, the total volume drawn over the course of the study should be approximately 146 mL. When more than 1 blood assessment is to be done at the time point/period, if they require the same type of tube, the assessments may be combined.

8. ADVERSE AND SERIOUS ADVERSE EVENTS ASSESSMENT

8.1 Definition of Adverse Events, Period of Observation, Recording of Adverse Events

An AE is any untoward medical occurrence in a clinical investigation subject administered a pharmaceutical product and that does not necessarily have a causal relationship with this treatment. An AE can therefore be any unfavorable and unintended sign (including an abnormal laboratory finding), symptom, or disease temporally associated with the use of a medicinal (investigational) product, whether or not related to the medicinal (investigational) product (ICH Guidance E2A 1995).

All AEs are collected from the time the informed consent is signed until the defined follow-up period stated in Section 7.1.4. This includes events occurring during the screening phase of the study, regardless of whether or not the IP is administered. Where possible, a diagnosis rather than a list of symptoms should be recorded. If a diagnosis has not been made, then each symptom should be listed individually. All AEs should be captured on the appropriate AE pages in the eCRF and in source documents. In addition to untoward AEs, unexpected benefits outside the IP indication should also be captured on the AE eCRF.

All AEs must be followed to closure (the subject's health has returned to his/her baseline status or all variables have returned to normal), regardless of whether the subject is still participating in the study. Closure indicates that an outcome is reached, stabilization achieved (the investigator does not expect any further improvement or worsening of the event), or the event is otherwise explained. When appropriate, medical tests and examinations are performed so that resolution of event(s) can be documented.

8.1.1 Severity Categorization

The severity of AEs must be recorded during the course of the event including the start and stop dates for each change in severity. An event that changes in severity should be captured as a new event. Worsening of pre-treatment events, after initiation of the IP, must be recorded as new AEs (for example, if a subject experiences mild intermittent dyspepsia prior to dosing of the IP, but the dyspepsia becomes severe and more frequent after first dose of the IP has been administered, a new AE of severe dyspepsia (with the appropriate date of onset) is recorded on the appropriate eCRF).

The medical assessment of severity is determined by using the following definitions:

Mild: A type of AE that is usually transient and may require only minimal treatment or therapeutic intervention. The event does not generally interfere with usual activities of daily living.

Moderate: A type of AE that is usually alleviated with specific therapeutic intervention. The event interferes with usual activities of daily living, causing discomfort but poses no significant or permanent risk of harm to the research subject.

Severe: A type of AE that interrupts usual activities of daily living, or significantly affects clinical status, or may require intensive therapeutic intervention.

[Appendix 4](#) provides criteria to assess the severity of liver-related adverse events.

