9.5 Planned Interim Analysis and Data Monitoring Committee

9.5.1 Planned Interim Analysis

Study enrollment will be paused after 92 subjects have been randomized in order for an IA to be conducted after at least 80 subjects have received 24 weeks of treatment. To protect study integrity, the IA will be performed by an independent statistician and statistical reporting group who are not involved in the clinical trial conduct and are not responsible for the final analysis of clinical trial data. The IA will be performed to evaluate the safety, tolerability, and efficacy of 3 doses of volixibat each compared to PBO and be used to drop 1 or more doses of volixibat, or to terminate the trial.

The criteria for deciding whether or not to continue randomizing to a particular volixibat dose following the Week 24 IA will be specified in the DMC charter. In general, randomization to any volixibat dose determined to be unsafe, intolerable or ineffective/futile at the IA will be discontinued. If all of the volixibat doses are determined to be intolerable or ineffective/futile the clinical trial will be terminated. If none of the volixibat doses are determined to be unsafe, intolerable or ineffective/futile then randomization to the volixibat dose that is the least promising or least helpful in characterizing the dose-response relationship (as specified in the DMC charter) will be discontinued. Tolerability will be assessed by comparing the number of discontinuations due to any one TEAE (presumably gastrointestinal events, most notably, diarrhea, loose stools, increased evacuations, and abdominal pain) between each volixibat dose group and PBO group. Efficacy will be assessed based on a reduction of steatosis (assessed by MRI-HFF) and ALT by comparing the change from baseline in MRI-HFF and percent change from baseline in ALT at Week 24 between each volixibat dose group and PBO group.

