9.9 Safety Analyses

The Safety Analysis Set will be used to assess the safety endpoints.

Adverse events will be coded using the Medical Dictionary for Regulatory Activities. Treatment-emergent AEs are defined as AEs that start or worsen on or after the date of the first dose of IP, and no later than the follow-up visit. The number of events, incidence, and percentage of TEAEs will be calculated by SOC, by preferred term, and by treatment group. Treatment-emergent AEs will be further summarized by severity and relationship to the IP. Adverse events related to the IP, AEs leading to withdrawal, SAEs, and deaths will be similarly summarized/listed.

Vital signs, ECG findings, and clinical laboratory tests will be summarized by treatment group and visit. Potentially clinically important findings will be summarized. Graphical presentation may be used when deemed necessary.

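### The rule that any change in AE severity opens a new event, combined with the TEAE definition, counts one episode several times and can make an easing pre-dose event treatment-emergent

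*Protocol*

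**What the plan says.** Three parts of the protocol (Amendment 2 text) act together.

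- **Recording.** Section 8.1.1 requires dated severity segments: "The severity of AEs must be recorded during the course of the event including the start and stop dates for each change in severity". It continues: "An event that changes in severity should be captured as a new event". No direction of change is named. The next sentence deals with events already present before treatment: "Worsening of pre-treatment events, after initiation of the IP, must be recorded as new AEs". It says nothing about improvement.
- **Collection period.** Section 7.2.3.3 states: "Adverse events are collected from the time informed consent is signed". Section 8.1 says the same and expressly includes the screening phase, so pre-dose AE records will exist and some may still be open at the first dose.
- **Analysis.** Section 9.9: "Treatment-emergent AEs are defined as AEs that start or worsen on or after the date of the first dose of IP", up to the follow-up visit. It then specifies: "The number of events, incidence, and percentage of TEAEs will be calculated by SOC, by preferred term, and by treatment group", with further summaries by severity and relationship.

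Nothing in the protocol shown links the severity segments of one episode, or keeps a segment that only improves out of the TEAE definition.

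**The concern.** A new event carries its own start date. Once every severity change opens a new event, the start condition in Section 9.9 is met by any segment that begins on treatment, whatever its direction. Two counts then no longer mean what a reader would take them to mean.

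1. The number of TEAEs becomes a count of severity segments, not of episodes.
2. An AE that was present before treatment and is getting better is reported as having emerged on treatment.

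Safety and tolerability against placebo is a secondary objective, and these tables describe it. Sites may also read the undirected wording differently, so the same clinical course could produce different numbers of records at different sites.

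**Working it through.** The plan gives no figure for this point, so there is none to reproduce. The check applies the recording rule and the TEAE definition literally to constructed histories. The histories are illustrations and do not come from the protocol.

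**Inputs**
- New record on any severity change, with its own dates: Section 8.1.1.
- Pre-dose AEs are recorded: Sections 7.2.3.3 and 8.1.
- TEAE if the AE starts or worsens on or after the first dose: Section 9.9.
- Both number of events and incidence are reported: Section 9.9.
- Assumption: incidence counts each subject once per term.

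**History A: moderate before the first dose, mild after it**
- Literal rule: the mild segment is a new AE with a post-dose start. TEAE records = 1; subjects with a TEAE = 1.
- If only worsening opens a new AE: no new record. TEAE records = 0; subjects = 0.
- Incidence for a term therefore rises by one subject, unless that subject already has another TEAE in the same term.

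**History B: one on-treatment diarrhoea episode, mild–moderate–mild**
- Severity changes k = 2.
- Literal rule: records = k + 1 = 2 + 1 = 3; subjects = 1.
- New record on worsening only: 1 + 1 worsening = 2; subjects = 1.
- One linked episode at maximum severity: records = 1; subjects = 1.

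**General form.** An on-treatment episode with k severity changes yields k + 1 TEAE events from one subject. The event count for that episode is multiplied by k + 1; incidence is not affected.

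**Summaries by severity.** If these are built from event records, history B puts one episode under both mild and moderate. If each subject is shown once at maximum severity, B is displayed correctly but A still appears, as a mild TEAE. Section 9.9 does not say which applies, so this effect is possible, not certain.

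**Was improvement meant to be included?** Setting the sentences side by side: if every change already opened a new event, the separate sentence on worsening of pre-treatment events would be largely redundant, and so would the worsening limb of the TEAE definition. That suggests the authors had worsening in mind. The recording sentence nevertheless has no such limit.

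**The case against.** **The text may mean worsening only.** The specific rule for pre-treatment events names worsening, and its one example runs from mild to severe. Section 8.1.3 also offers a recovering/resolving outcome for an event that is easing. This is a fair reading and it weakens history A: inclusion of improvement is inferred from the undirected word, not stated. It does not remove the problem. A site that follows the sentence as written will open the record, and even under the worsening-only reading history B gives 2 events.

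**The SAP can handle it.** Section 9.4 assigns safety definitions to the SAP, which is not shown, and the required start and stop dates keep the information needed to rebuild episodes. That stands as a route to a remedy. But the recording rule and the TEAE definition are fixed in the protocol, and as written they give these counts.

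**Some pre-dose conditions never become AEs.** Section 7.2.3.1 sends conditions present before randomization to medical history. This reduces the number of exposed records, but Section 8.1 still has screening-phase events recorded as AEs.

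**Inferences a reader might draw that the documents do not support**
- *That the inflation is greater in active or higher-dose arms because GI effects are dose-related and diminish.* Section 1.3 (Amendment 1 text) reports that the percentage of subjects with a GI TEAE generally rose with dose. It also says most events were mild and none severe. A mild event that diminishes has no lower grade on this three-level scale; it resolves without a new record. Frequent severity cycling is not shown.
- *That the interim tolerability decision is distorted.* Section 9.5.1 says "Tolerability will be assessed by comparing the number of discontinuations due to any one TEAE". A subject discontinues once, however many records the event has.
- *That pain from the screening biopsy would often supply history A.* The biopsy may predate screening by up to 6 months, and one done in screening must be early enough for its results to reach the site before baseline. The protocol gives no basis for treating this as common.

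**Conclusion.** The point holds as a defect in the stated counting rules for descriptive safety tables. Taken literally, Sections 8.1.1 and 9.9 turn one on-treatment episode into k + 1 TEAE events and turn an easing pre-dose AE into a TEAE. The first inflates event counts only. The second can also raise incidence, for subjects with no other TEAE in the category.

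The conclusion rests on two assumptions: that sites apply the undirected wording as written, and that no SAP rule collapses or reclassifies the records. How often severity changes, and how many AEs are open at the first dose and later ease, cannot be derived from the protocol. No overall percentage or between-arm bias should therefore be claimed. The primary and other efficacy analyses and the interim discontinuation comparison are unaffected. A correction is worth making because it is cheap and the tables concerned describe a secondary objective.

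**What to change.** 1. **Section 8.1.1.** State that a change in severity opens a new AE only when the event worsens. Alternatively, keep one record per severity level and link the records of one episode, either by an identifier on the eCRF or by a derivation from subject, preferred term and contiguous dates. Linking is the fuller remedy, since the worsening-only rule still gives 2 events in history B.
2. **Section 9.9.** Count a linked episode once, at its maximum on-treatment severity. Class it as a TEAE only if it first occurs on or after the first dose, or if its severity then exceeds its highest pre-dose severity.

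Under these rules history A gives 0 TEAEs and history B gives 1. The dates already required for each severity change are kept, so no severity history is lost. The cost is a wording change in two sections, one linking field or derivation with slight extra programming, and a minor clarification to sites.
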